9.6 Solicited Adverse Reactions and Grades

Table 9: Solicited Adverse Reactions and Grades

Reaction	Grade 0 (None)	Grade 1 (Mild)	Grade 2 (Moderate)	Grade 3 (Severe)	Grade 4 ¹ (Life-threatening)
Local					
Injection site pain	None	Does not interfere with activity	Repeated use of over-the-counter pain reliever > 24 hours or interferes with activity	Any use of prescription pain reliever or prevents daily activity	Requires emergency room visit or hospitalization
Injection site erythema (redness)	< 25 mm/ < 2.5 cm	25-50 mm/ 2.5-5 cm	51-100 mm/ 5.1-10 cm	> 100 mm/ > 10 cm	Necrosis or exfoliative dermatitis
Injection site swelling/induration (hardness)	< 25 mm/ < 2.5 cm	25-50 mm/ 2.5-5 cm	51-100 mm/ 5.1-10 cm	> 100 mm/ > 10 cm	Necrosis
Axillary (underarm) swelling or tenderness ipsilateral to the side of injection	None	No interference with activity	Repeated use of over-the-counter pain reliever > 24 hours or some interference with activity	Any use of prescription pain reliever or prevents daily activity	Emergency room visit or hospitalization
Systemic					
Headache	None	No interference with activity	Repeated use of over-the-counter pain reliever > 24	Significant; any use of prescription pain	Requires emergency room

Reaction	Grade 0 (None)	Grade 1 (Mild)	Grade 2 (Moderate)	Grade 3 (Severe)	Grade 4 ¹ (Life-threatening)
			hours or some interference with activity	reliever or prevents daily activity	visit or hospitalization
Fatigue	None	No interference with activity	Some interference with activity	Significant; prevents daily activity	Requires emergency room visit or hospitalization
Myalgia (muscle aches all over body)	None	No interference with activity	Some interference with activity	Significant; prevents daily activity	Requires emergency room visit or hospitalization
Arthralgia (joint aches in several joints)	None	No interference with activity	Some interference with activity	Significant; prevents daily activity	Requires emergency room visit or hospitalization
Nausea/vomiting	None	No interference with activity or 1-2 episodes/24 hours	Some interference with activity or > 2 episodes/24 hours	Prevents daily activity, requires outpatient intravenous hydration	Requires emergency room visit or hospitalization for hypotensive shock
Chills	None	No interference with activity	Some interference with activity not requiring medical intervention	Prevents daily activity and requires medical intervention	Requires emergency room visit or hospitalization
Fever (oral)	< 38.0°C < 100.4°F	38.0-38.4°C 100.4-101.1°F	38.5-38.9°C 101.2-102.0°F	39.0-40.0°C 102.1-104.0°F	> 40.0°C > 104.0°F

1. Grading of Grade 4 events will be determined per investigator and assessment is recorded on the reactogenicity event page in the electronic case report form.

Note: Events listed above but starting > 7 days post-study injection will be recorded on the AE page of the eCRF. Causality for each event will be determined per assessment by the investigator. Source: Guidance for Industry – Toxicity Grading Scale for Healthy Adult and Adolescent Volunteers Enrolled in Preventive Vaccine Clinical Trials (DHHS 2007).

9.7 Severity Grading of Vital Sign Abnormalities

Table 10: Severity Grading of Vital Sign Abnormalities

Vital Signs*	Mild (Grade 1)	Moderate (Grade 2)	Severe (Grade 3)	Potentially Life Threatening (Grade 4)
Fever (°C)** (°F)**	38.0 – 38.4 100.4 – 101.1	38.5 – 38.9 101.2 – 102.0	39.0 – 40 102.1 – 104	> 40 > 104
Tachycardia - beats per minute	101 – 115	116 – 130	> 130	ER visit or hospitalization for arrhythmia
Bradycardia - beats per minute***	50 – 54	45 – 49	< 45	ER visit or hospitalization for arrhythmia
Hypertension (systolic) - mm Hg	141 – 150	151 – 155	> 155	ER visit or hospitalization for malignant hypertension
Hypertension (diastolic) - mm Hg	91 – 95	96 – 100	> 100	ER visit or hospitalization for malignant hypertension
Hypotension (systolic) – mm Hg	85 – 89	80 – 84	< 80	ER visit or hospitalization for hypotensive shock
Respiratory Rate – breaths per minute	17 – 20	21 – 25	> 25	Intubation

* Participant should be at rest for all vital sign measurements.

** Oral temperature; no recent hot or cold beverages or smoking.

*** When resting heart rate is between 60 – 100 beats per minute. Use clinical judgement when characterizing bradycardia among some healthy participant populations, for example, conditioned athlete

9.8 Estimands and Estimand Specifications

Table 11: Intercurrent Events

Label	Intercurrent Event Type
IcEv1 (early discontinuation or unrelated death)	Early discontinuation from study or unrelated death prior to Day 29, the first post-treatment immunogenicity result available.
IcEv2 (alternative influenza vaccine)	Use of alternative Influenza vaccine prior to Day 29.
IcEv3 (COVID-19 vaccine)	Use of COVID-19 vaccine prior to Day 29.
IcEv4 (prohibited medications)	Use of prohibited medications deemed to impact on immunogenicity prior to Day 29.
IcEv5 (early infection)	Infection starting up to 29 days after IP injection.
IcEv6 (wrong vaccination)	Receiving wrong vaccination.

Abbreviation: IcEv: intercurrent event.

Table 12: Summary of Primary Immunogenicity Estimands with Rationale for Strategies to Address Intercurrent Events

Objective: To evaluate the humoral immunogenicity of mRNA-1010 relative to that of the active comparator against vaccine-matched influenza A and B strains at Day 29 based on HAI assays		
Estimand Label	Primary Immune Estimand 1a (on the PP Immunogenicity Set)	Supportive Immune Estimand 1b (on the Immunogenicity Set)
Estimand Description	Immune response to influenza measured as GMT ratio of anti-HA level as measured by HAI assay on Day 29 in adults aged 18 years or older who receive IP administration and complied with immunogenicity blood sampling to have a baseline and at least 1 post-injection antibody assessment without significant protocol deviations impacting immune response and RT-PCR-confirmed influenza between Days 1 to 29.	Immune response to seasonal influenza measured as GMT ratio of anti-HA level as measured by HAI assay on Day 29 in adults aged 18 years or older who receive IP administration irrespective of any significant protocol deviations impacting immune response and complied with immunogenicity blood sampling to have a baseline and at least 1 post-injection antibody assessment as measured by HAI assay.
Target Population	Adults aged 18 years or older who receive the assigned IP administration, complied with immunogenicity blood sampling to have a baseline and at least 1 post-injection serum antibody assessment as measured by HAI assay after the IP administration, and have no significant protocol deviations impacting the immune response and RT-PCR-confirmed influenza between Days 1 to 29.	Adults aged 18 years or older who receive any IP administration and complied with immunogenicity blood sampling to have a baseline and at least 1 post-injection antibody assessment as measured by HAI assay.
Endpoint	GMT ratio of anti-HA levels on Day 29	As per Estimand 1a.
Treatment Conditions	mRNA-1010 vs. active comparator (Fluarix Tetra)	As per Estimand 1a.

Population-Level Summary	Immune response to seasonal influenza defined as GMT ratio of anti-HA level as measured by HAI assay using an ANCOVA model on the log-transformed tiers on Day 29, with the vaccination group as the fixed variable, adjusted for stratified age group used for randomization and log-transformed baseline tiers.	As per Estimand 1a.
Intercurrent Event Strategy		
IcEv1 (early discontinuation or unrelated death)	Principal stratum	Principal stratum
IcEv2 (alternative influenza vaccine)	Principal stratum	Treatment policy
IcEv3 (COVID-19 vaccine)	Principal stratum	Treatment policy
IcEv4 (prohibited medications)	Principal stratum	Treatment policy
IcEv5 (early infection)	Principal stratum	Treatment policy
IcEv6 (wrong vaccination)	Principal stratum	Treatment policy

Rationale for Strategies	
This estimand seeks to understand immune response impact of influenza vaccine on adults aged 18 years or older who receive the IP administration and comply with key major protocol criteria.
 
A principal stratum is used for early discontinuation, unrelated deaths, early infection and significant deviations (such as use of alternative vaccines, COVID-19 vaccines, and prohibited medications) so that analysis is a sub-population composed of participants free from intercurrent events.
 
A treatment policy strategy is used for following up immune response including all participants vaccinated irrespective of whether they are administered wrong vaccination. The analysis of immune response is based on the randomized vaccine group.
	
A treatment policy strategy is used for following up immune response including all participants vaccinated irrespective of early infection or whether they subsequently were found not to strictly meet the key major protocol criteria (i.e. significant protocol deviations affecting immune response, use of the alternative influenza or COVID-19 vaccine, wrong vaccination or use of the prohibited medications). There is interest in understanding immune response in the light of poor compliance which may happen in clinical practice and may reflect reactions to the IP administration as well as poor compliance for unrelated reasons.
 
The principal stratum is employed for the other intercurrent events which match Estimand 1a.

Objective: to evaluate the humoral immunogenicity of mRNA-1010 relative to that of the active comparator against vaccine-matched influenza A and B strains at Day 29 based on HAI assays based on seroconversion rate		
Estimand Label	Primary Immune Estimand 2a (on the PP Immunogenicity Set)	Supportive Immune Estimand 2b (on the Immunogenicity Set)

Estimand Description	Immune response to influenza measured as seroconversion rate difference of antibody using HAI assay on Day 29 in adults aged 18 years or older who receive IP administration and complied with immunogenicity blood sampling to have a baseline and at least 1 post-injection antibody assessment without significant protocol deviations impacting immune response and RT-PCR-confirmed influenza between Days 1 to 29.	Immune response to influenza measured as seroconversion rate difference of antibody using HAI assay on Day 29 in adults aged 18 years or older who receive IP administration irrespective of any significant protocol deviations impacting immune response and complied with immunogenicity blood sampling to have a baseline and at least 1 post-injection antibody assessment.
Target Population	Adults aged 18 years or older who receive the assigned IP administration, complied with immunogenicity blood sampling to have a baseline and at least 1 post-injection antibody assessment after the IP administration, and have no significant protocol deviations impacting the immune response.	Adults aged 18 years or older who receive any IP administration and complied with immunogenicity blood sampling to have a baseline and at least 1 post-injection antibody assessment.
Endpoint	Seroconversion rate difference of antibody measured by HAI assay on Day 29.	As per Estimand 2a.
Treatment Conditions	mRNA-1010 vs. active comparator (Fluarix Tetra)	As per Estimand 2a.
Population-Level Summary	Immune response to influenza defined as seroconversion rate difference of antibody using Miettinen-Nurminen's method.	As per Estimand 2a.
Intercurrent Event Strategy		

IcEv1 (early discontinuation or unrelated death)	Principal stratum	Principal stratum
IcEv2 (alternative influenza vaccine)	Principal stratum	Treatment policy
IcEv3 (COVID-19 vaccine)	Principal stratum	Treatment policy
IcEv4 (prohibited medications)	Principal stratum	Treatment policy
IcEv5 (early infection)	Principal stratum	Treatment policy
IcEv6 (wrong vaccination) Rationale for Strategies	Principal stratum This estimand seeks to understand immune response impact of influenza vaccine on adults aged 18 years or older who receive the IP administration and comply with key major protocol criteria. A principal stratum is used for early discontinuation, unrelated deaths, early infection and significant deviations (such as use of alternative vaccines, COVID-19 vaccines, wrong vaccination, and prohibited medications) so that analysis is a sub-population composed of participants free from intercurrent events.	Treatment policy A treatment policy strategy is used for following up immune response including all participants vaccinated irrespective of early infection or whether they subsequently were found not to strictly meet the key major protocol criteria (i.e. significant protocol deviations affecting immune response, use of the alternative influenza or COVID-19 vaccine, wrong vaccination or use of the prohibited medications). There is interest in understanding immune response in the light of poor compliance which may happen in clinical practice and may reflect reactions to the IP administration as well as poor compliance for unrelated reasons. The principal stratum is employed for the other intercurrent events which match Estimand 2a.

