The mITT Set consists of all participants in the FAS who provide any follow-up for ILI beginning at least 14 days following administration of study intervention. Participants will be analyzed according to the group to which they are randomized to.

The mITT Set is the primary population for the analysis of efficacy data.

PP Set for Efficacy

The PP Set for Efficacy consists of all participants in the mITT Set who have no significant protocol deviations that impact key or critical efficacy data. Participants will be analyzed according to the group they are randomized to.

Immunogenicity Set

The Immunogenicity Set consists of all participants in the FAS who have baseline and Day 29 antibody assessment via HAI assay. Participants will be analyzed according to the group to which they were randomized.

PP Immunogenicity Set

The PP Immunogenicity Set includes all participants in the Immunogenicity Set who received planned dose of IP, complied with the immunogenicity testing schedule, and had no significant protocol deviations that impact key or critical data. Participants with RT-PCR-confirmed influenza between Days 1 to 29 will be removed from the PP Immunogenicity Set.

The PP Immunogenicity Set is the primary population for the analysis of immunogenicity data in the study unless specified otherwise. Participants will be analyzed according to the group to which they are randomized to.

For PP Set for Efficacy and PP Immunogenicity Set, the following major dosing error ranges for planned mRNA-1010 and active comparator will be used to determine participant exclusion from the analysis populations:

Table 3 Exclusion Criteria for Dosing Errors

Actual Vaccine Received	Planned (mRNA-1010 50 µg)
mRNA-1010 ≤ 37.5 µg	Yes ¹
mRNA-1010 >37.5 µg – 62.5 µg	No
mRNA-1010 > 62.5 µg	Yes
Active Comparator ²	Yes

1. Yes means major dosing error
2. Active comparator is Fluarix Tetra (pre-filled syringe)

Table 4 Major Dosing Errors for Active Comparator

Actual Vaccine Received	Planned (Active Comparator²)
Fluarix Tetra ≤ 45 µg	Yes ¹
Fluarix Tetra > 45 µg – 60 µg	No
Any mRNA-1010	Yes

1. Yes means major dosing error
2. Active comparator is Fluarix Tetra (pre-filled syringe)

Solicited Safety Set

The Solicited Safety Set consists of all randomized participants who received any study vaccination and contributed any solicited AR data, i.e., had at least one post-baseline solicited safety assessment.

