6.3 Immunogenicity Analysis

For immunogenicity analysis, antibody titers reported as below the LLOQ will be replaced by $0.5 \times$ LLOQ. Values that are greater than the ULOQ will be converted to the ULOQ.

The primary analysis population for immunogenicity will be the PP Immunogenicity Set, unless specified otherwise. In addition, the first 1000 randomized participants will also provide blood samples at Day 181 and Day 361 (Month 12), a subset of which will be used for immunogenicity analysis.

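### The early-infection exclusion for the primary immunogenicity estimands is worded inconsistently and tied to nominal Day 29 rather than to the participant's own blood sample

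*SAP*

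**What the plan says.** The exclusion appears in several places in the SAP.

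- **Section 9.8, Table 11, IcEv5:** "Infection starting up to 29 days after IP injection". No pathogen or test is named.
- **Section 5, PP Immunogenicity Set:** "Participants with RT-PCR-confirmed influenza between Days 1 to 29 will be removed from the PP Immunogenicity Set". Protocol Section 9.4 has the same rule.
- **Table 12, Estimand 1a (GMT ratio), target population:** participants must "have no significant protocol deviations impacting the immune response and RT-PCR-confirmed influenza between Days 1 to 29". The 1a description carries the same exclusion.
- **Table 12, Estimand 2a (seroconversion), description:** "without significant protocol deviations impacting immune response and RT-PCR-confirmed influenza between Days 1 to 29".
- **Table 12, Estimand 2a, target population:** the row stops at "and have no significant protocol deviations impacting the immune response", with nothing on influenza.

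The IcEv5 strategy is principal stratum for both 1a and 2a. Both estimands are labelled as being on the PP Immunogenicity Set, and SAP Section 6.3 states: "The primary analysis population for immunogenicity will be the PP Immunogenicity Set, unless specified otherwise".

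On timing, the Schedule of Events (Protocol Table 1, SAP Table 6) gives the Day 29 visit a window of 7 days early to 3 days late. IcEv2 to IcEv4 (other influenza vaccine, COVID-19 vaccine, prohibited medication) are also tied to Day 29 without reference to the sample.

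**The concern.** These rules decide who enters the primary set for all eight co-primary comparisons, so they should give one answer for each participant. Two things prevent that.

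**Scope.** Read literally, IcEv5 would also remove participants with COVID-19 or another infection, whereas Section 5 removes only confirmed influenza. The broad reading could be applied in practice, because swabs are also tested for SARS-CoV-2 and other respiratory pathogens. SAP Section 6.3.1 sends the reader to Table 12 for the detail of the estimands, and the SAP does not rank Section 5 above Tables 11 and 12.

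**Timing.** The purpose of the exclusion is to keep natural infection from contaminating the Day 29 titer. An infection that starts after the draw cannot do so, yet the Days 1 to 29 rule removes that participant. An infection on Day 30 or 31 before a Day 32 draw may do so, yet that participant stays. Removal after the draw is not neutral in principle. If a low titer predicts influenza, as the plan's use of HAI titer as a surrogate supposes, more low responders leave the less protective arm, and that arm's GMT and seroconversion rate rise. This would be anti-conservative if that arm were mRNA-1010.

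**Working it through.** **1. The plan's own figures.** SAP Section 4.3 gives 15% exclusion, 2550 per arm, true GMR 0.9, margin 0.667, SD 1.5 (natural log), seroconversion 70% (A) and 60% (B) with true difference 0, margin 10 points, and two-sided alpha 0.025 (z = 2.241).

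- PP set: 6000 × (1 − 0.15) = 5100, as stated.
- GMT: ln(0.9/0.667) = 0.2996; SE = 1.5 × √(2/2550) = 0.0420; 0.2996/0.0420 − 2.241 = 4.89. Power is 0.9999995 per strain and 0.999998 for four strains, taking the product.
- Seroconversion, A: SE = √(2 × 0.7 × 0.3/2550) = 0.01283; 0.10/0.01283 − 2.241 = 5.55.
- Seroconversion, B: SE = √(2 × 0.6 × 0.4/2550) = 0.01372; 0.10/0.01372 − 2.241 = 5.05. Power for four strains is 0.9999995.

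The stated power of at least 95% is reproduced with a wide reserve.

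**2. Days affected.** The draw can fall from Day 29 − 7 = 22 to Day 29 + 3 = 32.

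| Draw day | Later days on which influenza still excludes | Earlier days the Days 1 to 29 rule misses |
|---|---|---|
| 22 | 7 (Days 23–29) | 0 |
| 25 | 4 (Days 26–29) | 0 |
| 29 | 0 | 0 |
| 32 | 0 | 2 (Days 30–31) |

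**3. Number of participants.** The documents give no early-influenza rate. Assume 0.1% to 5% over Days 1 to 29, spread evenly. Total excluded: 5100 × 0.001 = 5 to 5100 × 0.05 = 255. If every draw were on Day 22, the share infected after sampling would be 7/29, that is 1 to 62 people. This is an upper bound. Removing all 255 leaves four-strain power at 0.999995 (GMT) and 0.999999 (seroconversion).

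**4. Effect of removing post-draw cases.** Let f = rate × 7/29 be the fraction removed from an arm. In the worst case none of them had seroconverted, and the arm's rate rises by p × f/(1 − f).

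| Assumed rates, arm 1 / arm 2 | f, arm 1 / arm 2 | Shift, A (p = 0.7) | Shift, B (p = 0.6) |
|---|---|---|---|
| 1% / 2% | 0.24% / 0.48% | 0.17 points | 0.15 points |
| 2% / 4% | 0.48% / 0.97% | 0.34 points | 0.29 points |
| 0% / 5% | 0 / 1.21% | 0.86 points | 0.73 points |

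For GMT, if those removed had 4-fold lower titers than their arm's average (assumed), the arm's mean log titer rises by ln 4 × f/(1 − f). At 0% / 5% this changes the GMR by a factor of exp(1.386 × 0.0122) = 1.017.

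**5. Effect of keeping influenza cases in the analysis.** If all infected participants stayed and all seroconverted, the difference moves by (1 − p) × (difference in rates).

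- 1% (mRNA-1010) against 2% (comparator): −0.3 points (A), −0.4 (B).
- 2% against 4%: −0.6 and −0.8 points.
- 0% against 5%: −1.5 and −2.0 points.

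With 4-fold higher titers in infected participants (assumed), the GMR factor is 4^(−0.01) = 0.986, 4^(−0.02) = 0.973 and 4^(−0.05) = 0.933. This is the cost of retaining every early case. The plan's gap on Days 30 and 31 would retain only a small part of them.

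**6. Scale.** The 97.5% CI half-width for seroconversion is 2.241 × SE = 2.9 points (A) and 3.1 points (B). The margin is 10 points.

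**The case against.** The strongest reply is that the SAP already has one operative rule. Section 5 gives the PP Immunogenicity Set a single definition and Section 6.3 makes it the primary population. Wherever the infection exclusion is spelled out in the set definition or the 1a and 2a rows, it is RT-PCR-confirmed influenza on Days 1 to 29. A fixed window is also simple and identical in both arms. The co-primary analyses are repeated on the Immunogenicity Set, with treatment policy for IcEv2 to IcEv6, so participants removed for early influenza reappear there if they have both titers.

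Most of this stands, and it rules out several stronger readings.

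- *The GMT and seroconversion co-primaries rest on different participants.* A reader might infer this from the 2a target population row. It would follow only if that row were programmed against the set definition, the 2a description and the 2a IcEv5 strategy, all of which keep the exclusion.
- *IcEv5 runs to Study Day 30.* The study-day formula in SAP Section 6.1 allows this reading. The same section, however, counts a period of up to 28 days after vaccination as the vaccination day plus 27 more, and on that convention IcEv5 ends on Day 29. A Day 30 conflict is not established.
- *A vaccine given after an early draw automatically removes the participant.* Protocol Section 6.5.2 says only that such use may affect evaluability. SAP Sections 5 and 6.2.5 require a significant deviation affecting key or critical data.

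Two things do not yield to the reply. A single Days 1 to 29 rule still misclassifies infections relative to the sample. The sensitivity analysis readmits all the other deviations together with the early infections, so it does not isolate this effect.

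**Conclusion.** The point holds as a matter of clear pre-specification and correct construction of the estimand. IcEv5, Section 5 and the 2a target population do not agree, and the nominal Day 29 anchor both removes participants whose titer was already fixed and keeps some whose titer may reflect infection.

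The expected effect is small. Even with the most extreme rates assumed above (0% against 5%), the seroconversion shift is below 0.9 points from removing post-draw cases and at most 2.0 points from keeping every early case, against a 10-point margin. Power is unaffected. A reader might infer that the non-inferiority conclusion is at risk, but nothing in the documents supports that.

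The sizes rest on assumptions outside the documents: the early-influenza rates, their even spread over days, every draw on Day 22, full seroconversion (or none) among those affected, and a 4-fold titer difference. No number is offered for the literal any-infection reading of IcEv5, because the documents give no rate for it. The timing argument also assumes that a draw anywhere in the Day 22 to 32 window counts as complying with the testing schedule.

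**What to change.** Before database lock, use one definition in SAP Section 5, in Table 11 (IcEv5), and in the description and target population rows of Estimands 1a and 2a: *RT-PCR-confirmed influenza with onset after injection and on or before the date of the participant's Day 29 immunogenicity sample.* This also supplies the missing exclusion in the 2a target population.

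Anchor the analysis definitions of IcEv2 to IcEv4 to the same sample date. This concerns the analysis sets only and changes no instruction to participants or sites.

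Protocol Section 9.4 carries the Days 1 to 29 rule, so record the change in SAP Section 7, which currently lists none.

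The cost is SAP wording and a small change to the analysis-set derivation. Injection, sample and illness-onset dates are already collected. A few participants infected after sampling stay in the PP Immunogenicity Set, and any infected between Day 29 and a later sample leave it.
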